8.3.5 Central Analysis of Secondary Endpoints

1. PPVs on a per-patient and per-region-basis of ⁶⁸Ga-PSMA-11 PET for detection of tumor location confirmed by histopathology/biopsy and conventional imaging follow-up will be calculated and reported along with the corresponding two-sided 95% confidence intervals. The confidence intervals will be constructed using the Wilson score method.
2. Sensitivity on a per-patient and per-region basis of ⁶⁸Ga-PSMA-11 PET for detection of tumor location confirmed by histopathology/biopsy will be summarized in tabular format. Ninety-five percent confidence intervals of sensitivity and PPV will be calculated using the Wilson score method.
3. Detection rates on a per-patient basis of ⁶⁸Ga-PSMA-11 PET stratified by PSA value (0.2 - <0.5, 0.5 - <1.0, 1.0 - <2.0, 2.0 - <5.0, 5.0) will be summarized in tabular format and compared between PSA strata using chi-square analysis.
4. The impact of ⁶⁸Ga-PSMA-11 PET on clinical management in BCR patients will be evaluated using surveys of the treating physician or practitioner before, at 1 (2-30 days) and 6 (range 3 - 12) months after the ⁶⁸Ga-PSMA-11 PET scan (see data collection sheet, section 44 eResearch). The results will be analyzed and provided in coded form for central analysis.
5. Safety will be reported descriptively as rates of patient reported adverse events.

9 Study Management

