2.2 Secondary

- Determine sensitivity and PPV on a per-patient and per-region-basis of ⁶⁸Ga-PSMA-11 PET/CT for detection of tumor location confirmed by conventional imaging, clinical follow-up, and histopathology/biopsy where available.
- Determine detection rates on a per-subject basis of ⁶⁸Ga PSMA-11 PET/CT stratified by PSA value (0.2 - <0.5, 0.5 - <1.0, 1.0 - <2.0, 2.0 - < 5.0, 5.0 or greater).
- Determine the impact of ⁶⁸Ga PSMA-11 PET/CT on clinical management in patients who have prostate cancer with biochemical recurrence.

- Continue to evaluate safety of ⁶⁸Ga-PSMA-11.

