2.3.2 Secondary Endpoints

- Per patient and per region detection sensitivity and PPV using a combined histology and conventional imaging correlate. *
- Change in management: survey based results. *
- Safety: blood pressure, heart rate, self-reported adverse events. *

Note: * secondary endpoints are assessed at central data analysis in the entire patient

Table 1	
Region	Description
1	Prostate Bed
2	Pelvis outside of prostate bed including lymph nodes
3	Extrapelvic soft tissue, lymph nodes and organ metastases (non-bone)
4	Bone metastases

population (n=1500) across participating institutions (see section 8.3.3)

3 Study Design

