5.3.1.3 Biopsy

Biopsies are performed to determine presence or absence of prostate cancer at the discretion of treating physicians according to standard of care.

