8.2 Determination of Sample Size and Accrual Rate

8.2.1 Sample Size and Power Estimate

The primary endpoint is to evaluate the positive predictive value (PPV) (true positives / (true positives + false positives)) of ⁶⁸Ga-PSMA-11 PET for presence or absence of prostate cancer

confirmed by histopathology on a per-patient basis. It is anticipated that – on a per-patient basis – the PPV of conventional imaging ranges between 30-50%. An overall PPV for ⁶⁸Ga-PSMA-11 PET of at most 50% will be considered as unacceptably low. Hence, the null hypothesis that the PPV is at most 50% will be tested against the alternative hypothesis that the PPV is greater than 50%.

Given recently published data from ⁶⁸Ga-PSMA-11 indicating a substantially higher PPV than previously assumed ⁴¹, we now hypothesize that ⁶⁸Ga-PSMA-11 PET imaging will substantially increase the PPV to at least 75% in our patient population.

We previously expected that approximately 25% of the accrued patients will undergo a biopsy and 95% of the biopsied patients will have positive ⁶⁸Ga-PSMA-11 PET scan at the biopsied site (about 5% of patients may receive a biopsy of a ⁶⁸Ga-PSMA-11 negative site, which was however identified on conventional imaging). However, we were able to obtain biopsies from ⁶⁸Ga-PSMA-11 positive lesions in only 13 of 316 evaluable subjects, and no biopsies of ⁶⁸Ga-PSMA-11 negative lesions identified by conventional imaging were obtained.

When 750 (instead of 375) patients are accrued at the University of Michigan, we now expect that about 24 patients who are to receive a biopsy will receive the biopsy of a ⁶⁸Ga-PSMA-11 positive lesion. Then, the attainable power is estimated at 80% for detecting an increase in the PPV from 50% to 75% at the one-sided 0.05 significance level.

Within the first secondary objective, the region-specific PPV will be determined (confirmed by conventional imaging, clinical follow-up, and/or histopathology/biopsy where available). Based on the results of previous studies, the following distribution of biopsied disease across the four regions are anticipated ^{1,2}:

- a) Prostate bed: 30%
- b) Pelvis: 15%
- c) Extrapelvic soft tissue: 20%
- d) Bone metastases: 35%

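### Section 8.3.5 item 2 measures sensitivity against histology alone, contrary to the composite reference in 2.2 and 2.3.2, and histology here samples almost only PSMA-positive disease

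*Combined protocol and SAP*

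**What the plan says.** The documents describe the reference standard for sensitivity in three places, and they differ.

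- **Section 2.2** sets sensitivity and PPV together, per patient and per region, "for detection of tumor location confirmed by conventional imaging, clinical follow-up, and histopathology/biopsy where available".
- **Section 2.3.2** lists the endpoint as "Per patient and per region detection sensitivity and PPV using a combined histology and conventional imaging correlate", to be assessed in the pooled "population (n=1500) across participating institutions (see section 8.3.3").
- **Section 8.3.5** splits the two measures. Item 1 (PPV) keeps histology plus conventional imaging follow-up. Item 2 (sensitivity) is "for detection of tumor location confirmed by histopathology/biopsy will be summarized in tabular format", with a 95% Wilson interval.

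On who is biopsied, section 5.3.1.3 leaves the decision "at the discretion of treating physicians according to standard of care". Section 5.1.1.2 (f) has the scan result shared with the patient's clinician. Section 8.3.4 c directs histological confirmation at PSMA-positive findings. Section 8.2.1 reports the yield so far: biopsies of PSMA-"positive lesions in only 13 of 316 evaluable subjects, and no biopsies of" PSMA-negative lesions identified by conventional imaging.

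Section 8.3.4 b describes one route to a false negative: biopsy of a lesion that is seen on conventional imaging and is negative on PSMA PET. Its follow-up imaging rules classify PSMA-positive lesions only.

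**The concern.** There are two linked problems.

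First, an analyst who follows item 2 reports a different quantity from the endpoint in 2.3.2. The denominators differ: patients or regions with histologically proven disease, against those with disease by histology or imaging.

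Second, the histology-only denominator is selected by the test under evaluation. Sensitivity needs the number of diseased patients or regions that the scan missed. If tissue is taken almost only where the scan is positive, missed disease does not enter the denominator and the estimate moves towards 100% whatever the true performance. A Wilson interval reflects sampling error among the verified cases. It does not reflect how they came to be verified.

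Section 1.1 says the pooled data are meant for an NDA submission. A sensitivity near 100% with a conventional interval could be taken at face value there.

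**Working it through.** The plan gives no sensitivity figure and no precision target for sensitivity, so there is no figure of its own to reproduce. The power statement in 8.2.1 concerns the primary PPV and does not enter here.

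**Step 1. Reference standards side by side**

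| Place | Measure | Reference |
|---|---|---|
| 2.2 | sensitivity and PPV | conventional imaging, clinical follow-up, histology where available |
| 2.3.2 | sensitivity and PPV | histology and conventional imaging |
| 8.3.5 item 1 | PPV | histology and conventional imaging follow-up |
| 8.3.5 item 2 | sensitivity | histology only |

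Only the last row drops imaging. Sections 2.2 and 2.3.2 also differ from each other on clinical follow-up.

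**Step 2. Item 2 applied to the site data in 8.2.1**

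Sensitivity = TP/(TP + FN). Inputs: 13 patients with a biopsied PSMA-positive lesion, and 0 biopsies of the kind that 8.3.4 b accepts as showing a false negative. So FN = 0 and sensitivity = TP/TP = 100% for any TP above zero. This takes it that no PSMA-negative disease was sampled by another route; the documents report none.

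The number of true positives among the 13 is not given. When all n are positive, the lower Wilson limit is n/(n + 1.96²) = n/(n + 3.84):

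- 10/10 (close to the hypothesised 75% PPV, 13 × 0.75 = 9.75): 10/13.84 = 72%, interval 72-100%.
- 13/13: 13/16.84 = 77%, interval 77-100%.

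For 750 patients the plan says "we now expect that about 24 patients who are to receive a biopsy will receive the biopsy of a" PSMA-positive lesion. If still no PSMA-negative lesion is sampled, the site result remains 100%, and only the lower limit rises:

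- 18/18 (24 × 0.75): 18/21.84 = 82%.
- 24/24: 24/27.84 = 86%.

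More biopsies of the same kind narrow the interval around 100% and add no information on misses.

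**Step 3. Partial rather than absent verification (illustration)**

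Let S be the true sensitivity, v the chance that PSMA-positive disease is biopsied, and r·v the chance for PSMA-negative disease. Both S and r are assumed. Histology is taken as correct, and selection is taken to depend on the PET result only. Then

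apparent sensitivity = S·v / (S·v + (1 − S)·r·v) = S / (S + (1 − S)·r).

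| r | S = 70% | S = 90% |
|---|---|---|
| 5% | 0.70/0.715 = 98% | 0.90/0.905 = 99% |
| 20% | 0.70/0.76 = 92% | 0.90/0.92 = 98% |
| 50% | 0.70/0.85 = 82% | 0.90/0.95 = 95% |
| 100% | 70% | 90% |

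The bias is upward for every r below 100% and vanishes at r = 100%.

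**Step 4. Does adding imaging to item 2 cure it?**

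Not alone. The imaging rules in 8.3.4 b start from a PSMA-positive lesion and call it true or false positive. None of them calls a PSMA-negative region a miss. Adding them to item 2 raises TP and leaves FN unchanged.

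**The case against.** **Item 2 agrees with 8.3.4 b.** That section names biopsy as the route to a false negative, so histology-only sensitivity could be deliberate, and amending 2.2 and 2.3.2 would also remove the contradiction. This partly stands: the documents do not show that a composite estimate would be less biased. But that route keeps an endpoint that cannot be estimated wherever no PSMA-negative site is sampled, which is the position this site reports.

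**The counts come from one site.** The endpoint is pooled, and no biopsy data from other sites are given. This stands. A reader might infer that the pooled sensitivity will be 100%, or will be inflated by a known amount. The documents support neither: they support a direction, on condition that other sites verify in a similar way. Nor do they support the inference that the pooled Wilson interval will exclude the true value, which depends on an unknown r and unknown counts.

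**A composite has its own errors.** This stands. Section 8.2.1 anticipates that "the PPV of conventional imaging ranges between 30-50"%, and section 1.2 describes low detection by bone scan and CT in this population. A reader might infer that moving to the composite removes the bias; it does not.

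**Baseline imaging may be missing.** A reader might assume that every patient has baseline conventional imaging on file. Section 5.3 commits only to imaging in the 12 months after the scan. Baseline conventional imaging is neither an eligibility criterion nor an item in Appendix 2, so a false-negative rule cannot depend on it.

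**Conclusion.** The contradiction is established from the text: item 2 does not estimate the endpoint in 2.2 and 2.3.2. It is an error in the rule as written rather than missing detail, and it should be fixed.

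On the data reported for this site, the rule returns 100% whatever the scan's true sensitivity. For the pooled 1,500, upward bias is expected if biopsy elsewhere is likewise discretionary, informed by the PET result and aimed at positive findings. Its size cannot be computed from the documents; the table in the working shows only how it varies with an assumed r. The planned interval does not allow for this selection.

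The scope is limited. Sensitivity is a descriptive secondary endpoint, and the primary PPV is not affected.

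**What to change.** 1. **Reconcile the reference.** Rewrite 8.3.5 item 2 to use the composite reference for the sensitivity endpoint, and align 2.2 and 2.3.2 on whether clinical follow-up counts.
2. **Write a false-negative rule for PSMA-negative regions** with that change. Base it on the conventional imaging and clinical notes that 5.3 already collects for 12 months after the scan, and use baseline imaging only where available. State a separate confirmation criterion for bone: 8.3.4 b iii has no size criterion, and its follow-up criteria ask for new findings, which a lesion already visible on the same modality cannot meet. Report regions without imaging as not verified.
3. **In either case, report histology-only sensitivity as counts**, with the number of PSMA-negative sites sampled, labelled as subject to verification bias, and not estimable where none was sampled.
4. **State the remaining limit**: the composite estimate may still be biased, because conventional imaging misses disease and confirmation is imperfect.

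Cost: no new patients, scans or biopsies. The rule has to be written and agreed with the pooled sites, and existing reports have to be classified: at most 1,500 × 4 = 6,000 regions, before removing those that are PSMA-positive or not imaged. Follow-up imaging is standard of care and locally read, so the data will be uneven. The reported sensitivity may be less favourable.

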9.1 Pre-study Documentation

This study will be conducted in accordance with the ethical principles that have their origin in the Declaration of Helsinki as stated in 21 CFR §312.120(c)(4); consistent with GCP and all applicable regulatory requirements.

Before initiating this trial, the Investigator will have written and dated approval from the Institutional Review Board for the protocol, written informed consent form, subject recruitment materials, and any other written information to be provided to subjects before any protocol related procedures are performed on any subjects.

The clinical investigation will not begin until either FDA has determined that the study under the Investigational Drug Application (IND) is allowed to proceed or the Investigator has received a letter from FDA stating that the study is exempt from IND requirements.

9.2 Institutional Review Board Approval

The protocol, the proposed informed consent form, and all forms of participant information related to the study (e.g. advertisements used to recruit participants) will be reviewed and approved by the University of Michigan Institutional Review Board (IRB) including the Protocol Review Committee (PRC). The initial protocol and all protocol amendments must be approved by the IRB prior to implementation.

9.3 Informed Consent

All participants must be provided a consent form describing the study with sufficient information for each participant to make an informed decision regarding their participation. Participants must sign the approved informed consent form prior to participation in any study specific procedure. The participant must receive a copy of the signed and dated consent document. The original signed copy of the consent document must be retained in the research file and a copy may be stored in the electronic medical record.

9.4 Changes in the Protocol

Once the protocol has been approved by the University of Michigan IRB, any changes to the protocol must be documented in the form of an amendment. The amendment must be submitted by the Investigator and approved by PRC and IRB prior to implementation.

If it becomes necessary to alter the protocol to eliminate an immediate hazard to patients, the study will be halted and the IRB will be informed within five (5) working days.

10 Protection of Human Subjects

10.1 Protection of Privacy

Patients will be informed of the extent to which their confidential health information generated from this study may be used for research purposes. Following this discussion, they will be asked to sign the informed consent document. The original signed document will become part of the patient's medical records, and each patient will receive a copy of the signed document. The use and disclosure of protected health information will be limited to the individuals described in the informed consent document.

Appendices

[figure not shown]
Appendix 1 Performance Status Criteria

ECOG Performance Status Scale		Karnofsky Performance Scale	
Grade	Descriptions	Percent	Description
0	Normal activity Fully active, able to carry on all pre-disease performance without restriction	100	Normal, no complaints, no evidence of disease
		90	Able to carry on normal activity; minor signs or symptoms of disease
1	Symptoms, but ambulatory Restricted in physically strenuous activity, but ambulatory and able to carry out work of a light or sedentary nature (e.g., light housework, office work)	80	Normal activity with effort; some signs or symptoms of disease
		70	Cares for self, unable to carry on normal activity or to do active work
2	In bed <=50% of the time Ambulatory and capable of all self-care, but unable to carry out any work activities Up and about more than 50% of waking hours	60	Requires occasional assistance, but is able to care for most of his/her needs
		50	Requires considerable assistance and frequent medical care
3	In bed >=50% of the time Capable of only limited self-care, confined to bed or chair more than 50% of waking hours	40	Disabled, requires special care and assistance
		30	Severely disabled, hospitalization indicated Death not imminent
4	100% bedridden Completely disabled Cannot carry on any self-care Totally confined to bed or chair	20	Very sick, hospitalization indicated Death not imminent
		10	Moribund, fatal processes progressing rapidly
5	Dead	0	Dead

Appendix 2 Schedule of Study Procedures and Assessments

Schedule of Study Procedures and Assessments				
Period/ Procedure	Screening	Imaging day 1	One day post imaging	Follow-up surveys
Study Day/Visit Day	-30 to 1	1	2 (allowed range day 2-4)	
Informed consent	X			
Laboratory values, history from medical record	X			
Pre-survey	X			
Performance status	X			
Blood Pressure, HR	X	X		
Imaging Procedure				
⁶⁸ Ga-PSMA-11		X		
PET/CT or PET/MRI		X		
Furosemide 20 mg IV		X		
Follow-up				
Adverse event reporting			X	
1. Post-survey (within 2-30 days of PET)				X
2. Post-survey (within 3-12 months of PET)				X

